## 13.Data Analysis

13.1 We will conduct a primary analysis per protocol and a secondary analysis per intention to treat. The rationale behind this strategy is to analyze both approaches and examine the result for consistency. A Repeated measures ANOVA analysis will be used for continuation of breastfeeding. To evaluate secondary outcomes between the two

**PROTOCOL TITLE:** Effect of immediate versus standard postpartum insertion of the contraceptive implant on breastfeeding outcomes

groups we will use the T-test, Wilcoxon Rank Sum test, Chi-squared test, or Fisher's exact test as appropriate. Secondary outcomes to be evaluated are to compare time of exclusivity of breastfeeding, mix breastfeeding, factors associated with discontinuing breasts feeding, time of breastfeeding discontinuation and patient satisfaction with postpartum contraception counseling and with timing of placing the implant between both groups. If there are significant differences between treatment groups, multivariable linear (for continuous outcomes) and logistic (for dichotomous outcomes) regression will be utilized in addition to control for confounding.

13.2 This study is a non-inferiority trial designed to demonstrate that immediate postpartum insertion of the ENG implant is non-inferior to standard ENG implant insertion with respect to the proportion of women who fail to breastfeed by 8 weeks after delivery. The failure rate for continuation of breastfeeding under the current treatment, standard insertion, is expected to be 30%.

The following sample size determination and plan for data analysis was developed in conjunction the University of New Mexico Clinical and Translational Science Center (CTSC). The non-inferiority margin for both primary outcomes is 15%, meaning that immediate insertion can be regarded as non-inferior (in terms of breastfeeding continuation) to standard insertion if the difference in rate with immediate insertion is no more than 15% worse than with standard insertion. To achieve 80% power with a 1-sided Type 1 error of 5% utilizing the Z test (unpooled) 62 participants are required in each group for a total 124. Accounting for the expected loss of follow up of 20%, the total subjects 149, round to 150. We intend to enroll up to 200 participants due to unanticipated loss to follow up, so this should ensure that we have enough data for data analysis.

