5. Factors associated with breastfeeding discontinuation: As mentioned previously, EBF is recommended for 6 months postpartum by the AAP and WHO. It is important to identify and acknowledge these factors to work and plan for counseling and initiatives to improve the length of lactation period. These factors can vary depending of society, culture and even mother's perception. Li et al reported the most common reasons for breastfeeding discontinuation during the first year postpartum were mothers' perception that their infant was not satisfied by breast milk alone and concerns about lactation and nutrition issue. In addition, mothers reported nipple biting and perceived infant loss of interest in breastfeeding (27). Odom et al, found in their study that factors such as difficulties with lactation, infant nutrition and weight, effort to pumping milk, among many others, play an important role in the decision making for lactation cessation (28). With this study, we aim to assess the reason for discontinuation in the mothers who use the implant as a contraceptive method.
6. Satisfaction with postpartum contraception counseling: The American College of Obstetricians and Gynecologists (ACOG) stated in Committee Opinion number 736: Optimizing Postpartum Care that as part of comprehensive postpartum care acknowledging women's reproductive life plan is of vital importance for decision making regarding contraception (1). We aim to explore by a survey how women perceived the counseling: if she understood the counseling and received enough information and time to make a decision about contraceptive choice. This might help to understand women's perception of counseling about postpartum contraception and may be helpful in improving current counseling.
7. Satisfaction with timing of contraceptive implant insertion: Early initiation of a contraceptive method has been recommended as an alternative by ACOG (1). This is because it has been proven that many women miss or do not have a postpartum follow up visit and it is more convenient for women to initiate a method early. When a contraceptive method is started in the postpartum period, it contributes to birth spacing, and maternal and infant wellbeing. We look to understand the satisfaction with having an implant inserted early vs having it inserted in the standard time.

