## **15. Withdrawal of Subjects**

- 15.1 The research team will provide thorough screening to see if the patient will meet inclusion and exclusion criteria. If any circumstances arise such participant experiencing exclusion criteria during study participation or fail to follow study procedures such as having the implant placed or removed before the study ends, the participant will be notified and withdrawn from the study without their consent.
- 15.2 Participants may have their implant removed at their request at any time. However, removal of the implant automatically terminates participation in the study and no data will be collected further. The data that was already collected from those participants that withdraws or was withdrawn from the study will be used for data analysis.
- 15.3 NA
- 15.4 Participants may withdraw from study involvement at any point in time and this will not affect their ability to obtain standard clinical care that day. All data points will be collected on the date of the procedure and therefore we anticipate loss to follow up and withdrawal rates will be low. Participants will be given the information on how to withdraw in the study consent.
- 15.5 The authorization for the use and disclosure of the participant health information for this study shall not expire unless the participant cancels this authorization. The health information will be used or disclosed as long as it is needed for this study. However, the participant may withdraw her authorization at any time providing a notification to the UNM investigators in writing to notifying the study team about the withdrawal. To do this, a letter should be sent to:

[name]  
Department of Obstetrics and Gynecology  
[name]  
[name]

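### Per protocol is the sole primary analysis, and nothing requires intention to treat to meet the 15-point margin before non-inferiority is claimed

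*Combined protocol and SAP*

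**What the plan says.** Section 13.1 (Data Analysis) names the analysis sets: "We will conduct a primary analysis per protocol and a secondary analysis per intention to treat". The reason follows: "The rationale behind this strategy is to analyze both approaches and examine the result for consistency". It gives no rule for disagreement, and no section defines the per-protocol set.

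Section 13.2 sets the margin ("The non-inferiority margin for both primary outcomes is 15" percent) and the expected standard-arm discontinuation ("standard insertion, is expected to be 30" percent). On sample size it says: "To achieve 80% power with a 1-sided Type 1 error of 5% utilizing the Z test (unpooled) 62 participants are required in each group".

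Three other places bear on who might leave the per-protocol set:

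- Section 2.3, secondary objectives, item 7, argues for early insertion partly because "many women miss or do not have a postpartum follow up visit". It gives no rate.
- Section 15.1 withdraws women who "fail to follow study procedures such as having the implant placed or removed before the study ends". I read this as covering both failure to have the implant placed and early removal. Section 15.2 ends data collection once the implant is removed. Data gathered before a withdrawal are kept for analysis.
- Section 12 books standard insertion at 4 weeks so that two weeks remain for rescheduling, with a reminder a week beforehand. For the immediate arm it provides round-the-clock cover to meet the 24-hour window.

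**The concern.** A per-protocol comparison is no longer a comparison of randomised groups if the reasons for exclusion differ by arm and are related to the outcome. Here the opportunities to deviate differ. Immediate insertion takes place in hospital within a day of birth. Standard insertion needs an outpatient return weeks later, while the 8-week feeding outcome is still accruing. Women who do not return may feed their infants differently from those who do.

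If so, the per-protocol difference departs from the randomised difference by an unknown amount in an unknown direction. As written, the per-protocol upper limit could fall below 15 points while the intention-to-treat limit does not, and the plan does not say which result stands. Since per protocol is the only analysis called primary, it would be the natural basis for the claim.

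**Working it through.** **Inputs from section 13.2.** Margin 0.15; standard-arm discontinuation 0.30; one-sided alpha 0.05 (z = 1.645); unpooled Z test; 62 evaluable per arm. Section 13.1 gives no decision limit, so I take the claim rule to be that the upper one-sided 95% limit for the difference in discontinuation (immediate minus standard) lies below 0.15.

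**The plan's own figure.** n per arm = (1.645 + 0.842)² × [p_I(1 − p_I) + p_S(1 − p_S)] / (0.15 − difference)².

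- Equal rates of 30%: 6.18 × 0.42 / 0.0225 = 115.4, so 116 per arm. The stated 62 is not reproduced.
- Immediate 25%, standard 30%: 6.18 × 0.3975 / 0.04 = 61.4, so 62. The documents do not state that assumption.

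This is a separate matter and does not decide the present point. I keep 62 per arm below because it is the planned figure.

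**Assumptions, because the documents give no rates.** A fraction m of the standard arm is excluded from per protocol, those women discontinue at rate q, and nobody in the immediate arm is excluded. The 20% used for m is not the plan's 20% loss to follow-up.

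**Step 1: false claims at the margin (true 45% v 30%).**

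- Standard rate among those kept: p_PP = (0.30 − m·q) / (1 − m).
- Chance of a claim: Φ[(0.15 − (0.45 − p_PP)) / SE − 1.645], with SE² = 0.45 × 0.55/62 + p_PP(1 − p_PP)/(62(1 − m)).
- Intention to treat gives 5.0%.
- Example, m = 20%, q = 10%: p_PP = (0.30 − 0.02)/0.80 = 0.35; SE = √(0.2475/62 + 0.2275/49.6) = 0.0926; 0.05/0.0926 − 1.645 = −1.105; Φ = 13.5%.

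| q, with m = 20% | Standard rate kept | Difference | Chance of false claim |
|---|---|---|---|
| 10% | 35.0% | 10.0 points | 13.5% |
| 20% | 32.5% | 12.5 points | 8.5% |
| 30% | 30.0% | 15.0 points | 5.0% |
| 40% | 27.5% | 17.5 points | 2.7% |
| 50% | 25.0% | 20.0 points | 1.3% |

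As m goes from 10% to 40%, the false-claim rate runs from 8.2% to 36.3% at q = 10%, and from 2.1% to below 0.1% at q = 60%.

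**Step 2: no true difference (30% v 30%).** Intention to treat claims with probability 57%. Per protocol at m = 20% claims with probability 53% if q = 30%; this drop comes from the smaller group alone. At q = 50% it claims with probability 32%.

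**Step 3: a data set in which the analyses disagree.**

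- Intention to treat, 21/62 v 19/62 stopped: difference 3.2 points, SE 8.39, upper limit 3.2 + 1.645 × 8.39 = 17.0. No claim.
- Per protocol after dropping 16 standard-arm women, 2 of whom had stopped, 21/62 v 17/46: difference −3.1, SE 9.32, upper limit 12.2. Claim.
- If 8 of the 16 had stopped, 21/62 v 11/46: difference 10.0, SE 8.70, upper limit 24.3. Per protocol fails by more than intention to treat.

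**Step 4: effect of requiring both sets.** Binomial simulation with 62 immediate, 50 standard kept and 12 standard dropped:

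- True 45% v 30%, q = 10%: false claims fall from about 13% to about 5%.
- 30% v 30%, q = 30%: claims go from about 52% to 49%.
- 30% v 30%, q = 50%: about 30% with or without the rule.

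**The case against.** A reader might infer that the claim rests on per protocol alone and stands whatever intention to treat shows. The documents do not say that: intention to treat is planned, and comparing the two is the stated purpose. The plan is silent on disagreement. Per protocol as primary with an intention-to-treat check is also a recognised choice for non-inferiority, not an error in itself.

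A reader might also infer that exclusions will fall mainly on the standard arm. That is plausible but undocumented. The remark about missed visits concerns postpartum women generally, and section 12 provides reminders, rescheduling and, at UNM, an alternative clinic. The immediate arm has its own routes to exclusion: a missed 24-hour window, limits on insurance cover and free implants (section 22), and removal, with more time before week 8 in which it can happen. If the immediate arm also lost 10% or 20%, with those women discontinuing at 25%, the 13.5% would become 8.8% or 5.0%.

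Finally, 13.5% requires women who miss insertion to continue breastfeeding far more often than those who attend (90% v 65%). If they continue less often, per protocol is conservative.

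These points stand and limit the size of the concern. They do not supply the missing decision rule or the missing per-protocol definition.

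**Conclusion.** The gap is real and worth closing, as a cheap improvement rather than a fatal flaw. Per protocol is the sole primary analysis, its population is undefined, and intention to treat has no deciding role, so non-inferiority could be claimed per protocol when intention to treat fails.

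With one-fifth of the standard arm excluded and none of the immediate arm, the false-claim rate at the margin ranges from 1.3% to 13.5% as the excluded women's discontinuation goes from 50% down to 10%, against 5.0% for intention to treat. The exclusion fraction, the excluded women's rates and the absence of immediate-arm exclusions are assumptions. The documents do not support a reading that the bias favours non-inferiority; they support only that its direction cannot be known beforehand.

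**What to change.** State in 13.1 that non-inferiority is claimed only if the upper one-sided 95% confidence limit for the difference in 8-week discontinuation (immediate minus standard) is below 15 points in both the intention-to-treat set (all randomised women, by assigned group) and the per-protocol set.

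Three additions make the rule workable:

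- Define the per-protocol set before analysis.
- Report exclusions by arm.
- Reconcile 15.1 and 15.2 with the intention-to-treat analysis, so that 8-week feeding status is obtained for every randomised woman whatever her insertion status. The retrospective survey and chart review in section 12 already offer a means. As written, withdrawal may cut off data on exactly the women at issue.

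Both analyses are already planned, so the cost is a few sentences, some follow-up effort, and a fall in the chance of a claim from about 52% to 49% when there is neither a true difference nor selection. The rule protects against false claims only. It does not restore power if selection makes immediate insertion look worse.

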  - 1.3.1. Secondary Objective 1: To compare the total number of days of postpartum bleeding in the immediate versus standard group at 2, 4, and 8 weeks postpartum . Our hypothesis is that number of days of bleeding in the immediate insertion group is not significantly different than the number of days of bleeding in the standard insertion group.
  - 1.3.2. Secondary Objective 2: To compare postpartum sexual function as measured by Female Sexual Function Index (FSFI) score at 4, 8, and 12 weeks postpartum. Our hypothesis is that FSFI scores for the immediate insertion group are not significantly different than FSFI scores for the standard insertion group.

PROTOCOL TITLE: Effect of immediate versus standard postpartum insertion of the contraceptive implant on breastfeeding outcomes

- 1.3.3. Secondary Objective 3: To compare postpartum mood as measured by EPDS score at 2, 4, and 8 weeks postpartum. Our hypothesis is that EPDS scores for the immediate insertion group are not significantly different than EPDS scores for the standard insertion group.
- 1.3.4. Secondary Objectives 4: To compare exclusive breastfeeding through 6 months postpartum between the immediate versus the standard group.
- 1.3.5. Secondary Objective 5: To compare postpartum factors associated with discontinuing breastfeeding between the immediate versus the standard group.
- 1.3.6. Secondary Objective 6: To compare timing of breastfeeding discontinuation through 6 months postpartum between the immediate versus the standard group.
- 1.3.7. Secondary Objective 7: To compare participant satisfaction with postpartum contraception counseling in women enrolled in the study and in those women who opted not to enroll in the study.
- 1.3.8. Secondary Objective 8: To compare participant satisfaction with timing of ENG implant insertion between the immediate versus the standard group.

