**Regarding secondary objectives:**

1. Bleeding patterns: Irregular bleeding is the most common side effect noted by users of the ENG contraceptive implant. Limited evidence shows that this holds true in the postpartum period (17). In a retrospective cohort study of women who underwent immediate versus standard postpartum insertion of the implant, approximately one in five women requested discontinuation of use due to irregular bleeding, and this rate was not significantly different between the two groups (17). Evidence on the effect of immediate postpartum insertion of the ENG contraceptive implant on lochia is limited and mixed. An RCT of immediate versus standard postpartum insertion of the six-rod levonorgestrel implant showed significantly more total days of bleeding for the immediate insertion group (18), while a more recent Australian prospective cohort study demonstrated no lengthening of the duration of lochia (postpartum bleeding) with immediate insertion (19). We will measure postpartum bleeding patterns using periodic review of a patient bleeding diary that quantifies bleeding on a daily basis as “none”, “spotting”, “bleeding” or “heavy bleeding”. As patient dissatisfaction with irregular bleeding likely mediates discontinuation for this reason, we will also measure patient satisfaction with their bleeding pattern postpartum.

PROTOCOL TITLE: Effect of immediate versus standard postpartum insertion of the contraceptive implant on breastfeeding outcomes

2. Postpartum mood changes: It is possible that postpartum use of an ENG implant may affect postpartum mood. In a retrospective study of adverse event reporting for ENG implant use, it was noted that postpartum depression was a commonly reported adverse event, and therefore may be associated with implant use in the postpartum period (20). In addition, in a secondary analysis study, use of the ENG implant in the postpartum period was associated with a higher risk of later antidepressant use compared to women with no hormonal contraceptive use (21). Women's perception of contraceptives' effect on their mood is a significant factor in contraception discontinuation (22). We hypothesize that timing of implant insertion will not increase postpartum depression related mood changes as measured by the EPDS. We will also assess patient perception of impact of ENG implant insertion on mood.

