## 7. Study Endpoints

	Screen -ing	First 24 hours Post partu m	1-7 days*	2 weeks	4 weeks	6 weeks	8 weeks	12 weeks	24 weeks END	Up to 1 year pp	Up to 5 years pp
Intake	X										
Postpartum contraception counseling satisfaction survey	X				X						
Device Insert		X			X	X					
Exclusive breastfeeding			X	X	X		X	X	X		
Breastfeeding discontinuation				X	X		X	X	X		
Retrospective Breastfeeding Discontinuation Chart Review Form										X	
Contraceptive use			X		X		X	X	X		X
Diary collection				X	X		X				
Mood (EPDS)				X	X		X				
Sexual function (FSFI)					X		X	X			
Bleeding log review				X	X		X				

7.1. The primary endpoint of this research are to compare continuation of lactation at eight week postpartum between women in the immediate with standard group.

The secondary endpoints of this research are to compare number of days of postpartum bleeding, postpartum sexual function as measured by FSFI score, and postpartum mood as measured by EPDS score, time to resumption of sexual activity, exclusive breastfeeding method, factors associated with discontinuing breastfeeding, timing of breastfeeding discontinuation, patient satisfaction with postpartum contraception counseling and the implant and patient satisfaction with bleeding pattern between the immediate and standard insertion groups.

As in other studies of breastfeeding and hormonal contraception, we will continue to follow women out to 6 months. A survival analysis will be performed to determine longer-term effect of hormonal contraception on breastfeeding.

**PROTOCOL TITLE:** Effect of immediate versus standard postpartum insertion of the contraceptive implant on breastfeeding outcomes

- 7.2. The primary study endpoint is also a safety endpoint: breastfeeding continuation through 8 weeks. We have developed a Data Safety and Monitoring Plan related to these endpoints (please see below).
- 7.3. No exploratory endpoints will be conducted in this research.

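### Section 13.1 puts per protocol first without confining it to the breastfeeding non-inferiority endpoint, so an undefined set selected after randomisation also appears to lead the secondary outcomes tested for a difference

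*Combined protocol and SAP*

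**What the plan says.** Section 13.1 opens with "We will conduct a primary analysis per protocol and a secondary analysis per intention to treat" and gives the reason: "The rationale behind this strategy is to analyze both approaches and examine the result for consistency". Neither sentence names an outcome. The same paragraph then gives a method for breastfeeding continuation and a choice of two-group tests for secondary outcomes. Its own list begins "Secondary outcomes to be evaluated are to compare time of exclusivity of breastfeeding, mix breastfeeding, factors associated with discontinuing breasts feeding" and continues with timing of discontinuation and two satisfaction items. Bleeding days, EPDS and FSFI are not in that list.

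Section 7.1 does make them secondary endpoints: "The secondary endpoints of this research are to compare number of days of postpartum bleeding, postpartum sexual function as measured by FSFI score", with EPDS later in the same sentence. Section 1.3.1 gives the bleeding hypothesis, with the standard arm as comparator: "Our hypothesis is that number of days of bleeding in the immediate insertion group is not significantly different than the number of days of bleeding". Sections 1.3.2 and 1.3.3 use the same form for FSFI and EPDS. No margin is given for any of the three.

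The per-protocol set is defined nowhere. The nearest guide is section 15.1, which has the study team withdraw participants who "fail to follow study procedures such as having the implant placed or removed before the study ends". The natural reading is failure to have the implant placed, or early removal. Section 15.2 ends data collection at removal but adds: "The data that was already collected from those participants that withdraws or was withdrawn from the study will be used for data analysis". It does not say in which analysis set.

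**The concern.** Leading with per protocol can be argued for a non-inferiority test, where non-adherence can make the arms look alike. That argument does not carry over to outcomes tested for a difference, where analysis by randomised group is the usual lead.

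The protocol itself links removal to these outcomes. Section 2.3 says that dissatisfaction with irregular bleeding probably drives discontinuation, that perceived mood effects are an important reason for stopping contraception, and that in a cited study a perceived negative effect on sex life was the strongest predictor of discontinuation. A set without removals is therefore selected on something related to the outcome being compared.

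The opportunity for exclusion also differs by arm. The immediate arm can have removals from the first day. The standard arm can have them only after insertion at 4-6 weeks, but it is more exposed to non-placement, since section 2.3 notes that many women miss the postpartum visit. The week-2 EPDS and the 2- and 4-week diaries largely precede standard insertion. A standard-arm woman could therefore be left out of a week-2 comparison because of a visit she missed later.

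Because the hypotheses are of no significant difference and have no margin, any dilution of a true harm moves the result towards the one hoped for.

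**Working it through.** **Plan figures.** The plan states no sample size, power or SD for bleeding days, EPDS or FSFI, so there is nothing to reproduce. Its sample size belongs to the breastfeeding endpoint and is not used below, except for the target of 75 per arm (section 5.3).

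**Step 1: time at risk of removal.** By week 8 an immediate-arm woman has had the implant for about 8 weeks. A standard-arm woman has had it for 8 - 6 = 2 to 8 - 4 = 4 weeks. Some asymmetry is plausible, but the plan gives no removal rates by week 8.

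**Step 2: worst-case shift in bleeding days.** Assumptions, none from the documents: normal outcome, SD 12 days in both arms, and the women removed are exactly those with the most bleeding. Excluding the top fraction p lowers an arm's mean by SD × φ(z)/(1 - p), where z is the upper p point of the standard normal and φ its density.

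| Removed, immediate v standard | Shift in each arm (SD) | Net (SD) | Net at SD 12 |
|---|---|---|---|
| 5% v 2% | 0.109 v 0.049 | 0.059 | 0.7 days |
| 10% v 3% | 0.195 v 0.070 | 0.125 | 1.5 days |
| 20% v 5% | 0.350 v 0.109 | 0.241 | 2.9 days |

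With equal removal rates and equal SDs the net shift is zero.

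**Step 3: relax the worst case.** If removal correlates only ρ with the outcome, each shift is multiplied by ρ. At ρ = 0.3 the three rows become 0.3 × 0.7 = 0.2, 0.3 × 1.5 = 0.45 and 0.3 × 2.9 = 0.9 days.

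**Step 4: effect on detecting a harm.** Assume 75 per arm, a true excess of 0.5 SD in the immediate arm, a two-sided 5% test, and a share q excluded from the immediate arm only. With s = ρ × φ(z)/(1 - q), power = Φ[(0.5 - s)/√(1/75 + 1/(75(1 - q))) - 1.96]. With everyone included it is Φ(0.5/√(2/75) - 1.96) = 0.87.

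| q | s, ρ = 0.3 to 1.0 (SD) | Power, ρ = 0.3 to 1.0 |
|---|---|---|
| 5% | 0.03 to 0.11 | 0.81 to 0.66 |
| 10% | 0.06 to 0.20 | 0.75 to 0.44 |
| 20% | 0.11 to 0.35 | 0.63 to 0.14 |

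Exclusion from one arm only and ρ = 1 are both extremes.

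**Step 5: what analysis by randomised group can recover.** Under section 15.2 a woman whose implant is removed at day 28 has no later diary and no week-8 EPDS or FSFI. If she bled every day she contributes 28 days to a total, against a possible 56 (8 × 7) for a woman followed throughout. A raw total over unequal diaries can therefore understate bleeding even when she stays in the analysis.

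**The case against.** A reader might infer that section 13.1 makes per protocol the main analysis for every outcome, that women with removal or non-placement are dropped, and that this hides harm. The documents do not support that much:

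- Section 13.1 never says that the rule covers every outcome, and its list of secondary outcomes omits bleeding days, EPDS and FSFI. One listed item, satisfaction with counselling, is in section 1.3.7 a comparison of enrolled with non-enrolled women, to which the choice of set does not apply.
- The exclusion is inferred from a withdrawal rule. The set is undefined, and section 15.2 keeps data already collected, so a per-protocol analysis using records up to removal is equally open.
- The cited cohort, in which "approximately one in five women requested discontinuation of use due to irregular bleeding", found no significant difference in that rate between the timing groups. This is the only between-group removal evidence in the documents, and it does not support unequal rates such as 10% v 3%.
- Analysis by intention to treat is planned and will be compared with per protocol, so a disagreement would be visible.
- Changing the order of the analyses cannot restore data that section 15.2 stops collecting.

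All of this stands and limits the claim. It does not remove it. The rule is unscoped, and the tests in that paragraph are the only analysis text that can apply to bleeding days, EPDS and FSFI. The cohort's follow-up window is not given, so it does not settle removals by week 8. Section 13.1 has no rule for deciding when the two sets disagree, and it labels per protocol as primary.

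**Conclusion.** The point holds as a defect of scope and definition that should be corrected. As written, an undefined set that section 15.1 suggests is selected after randomisation takes the lead for between-arm secondary outcomes tested for a difference, although the reasons for exclusion are related to those outcomes and arise unequally by arm. This can dilute a harm; the documents do not show that it will, nor by how much. The 0.7 to 2.9 days rest on an assumed SD of 12, assumed unequal removal rates, and removal of exactly the heaviest bleeders. Weaker correlation shrinks them and equal rates give zero. The dilution of 0.03 to 0.35 SD in Step 4 assumes exclusions from the immediate arm only. The effect of excluding non-placed women in the standard arm is not quantified, and its direction is unknown. The point does not touch the choice of lead set for the 8-week non-inferiority claim.

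**What to change.** In section 13.1:

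1. Confine the per-protocol-first rule to the 8-week breastfeeding non-inferiority endpoint.
2. State that the between-arm secondary outcomes, naming bleeding days, EPDS, FSFI, and satisfaction with implant timing and bleeding, are analysed mainly by randomised group, using all records collected, including those before removal or withdrawal. Per protocol is supportive for these.
3. Define the per-protocol set: how non-placement, late placement and removal are handled, and whether records before the event count.
4. Analyse bleeding so that shortened diaries are allowed for, for example as bleeding days per observed day or by 2-, 4- and 8-week interval.
5. State that outcomes after removal are missing under section 15.2, and that analysis by randomised group does not recover them.

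The cost is a few sentences and slightly more analysis work. Both analyses are already planned, and no extra participants or data are needed. The gain is greatest for the 2- and 4-week records, which largely precede standard insertion. The gap after removal remains.
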